## 12.7.4 Safety Evaluation

Safety variables monitored in this study include: AEs; spirometry (clinical interpretation and COPD categories) and respiratory symptoms (cough assessment VAS and Likert scales); vital signs (systolic and diastolic blood pressure, pulse rate, respiratory rate); ECG data; concomitant medications, clinical chemistry, hematology, urine analysis safety panel; physical examination, body weight, and BMI.

### 12.7.4.1 Safety Reporting

All safety data collected during the study will be provided in listings by randomization arm, site, subject, and product use pattern category defined over the 12-month period. Safety study periods are defined as follows:

- Screening: [Screening to V3[
- Product Trial: [V3 to V4]
- Exposure: ]V4 to V16]
- Safety Follow-up: [Start to End of Safety Follow-up], where
  - the Start of Safety Follow-up is after Completion of V10 for subjects who complete the main study but do not enroll in the extension study, after Completion of V16 for completers of the extension study, or after the latter of the discontinuation date and the Early Termination visit date for non-completers

All summaries for safety parameters will be conducted on the Safety Population. Unless otherwise specified, summaries will be produced overall by randomization arm and product use pattern categories (see Section 4.1.2 “Definition of Product Use Pattern Categories”).

Safety data collected during the Product Trial period will be summarized by randomization arm in a separate table, including subjects in the Safety population who are not randomized.

AEs occurring during the safety follow-up will be summarized accounting for the number of subjects entered in the safety follow-up period.

Unless otherwise specified, safety data collected during the Screening period will be provided in listings only.

### **12.7.4.2 Adverse Events**

A product emergent AE is defined as an AE that occurs at Enrollment or later. AEs that occurred at Enrollment will be considered product emergent only if flagged as having started after first THS 2.2 use in the eCRF. All other AEs will not be summarized but provided in listings only. Additionally, product emergent AEs flagged as having occurred after THS 2.2 use or with a start date greater than any recorded THS 2.2 use date will be summarized during the Product Trial period.

Any new, clinically relevant, abnormal finding or worsening of a pre-existing condition/concomitant disease detected during the study including the safety follow-up period will be documented as an AE and/or SAE as described in the Safety Management Plan.

All AEs occurring from the signing of informed consent will be recorded electronically. AEs collected before product use will be provided in listings only.

#### **12.7.4.2.1 All Adverse Events**

General AEs summary tables will be presented for:

- The number of events and the number and percentage of subjects reporting at least one AE.
- The number of events and the number and percentage of subjects reporting at least one study product-related AE, broken down by product relatedness (related to THS 2.2/CC) and expectedness (expected for THS 2.2 / CC).
- The number of events and the number and percentage of subjects with at least one AE leading to study discontinuation.
- The number of events and the number and percentage of subjects reporting at least one AE broken down by severity including each subject only once with the worst severity.
- The number of events and the number and percentage of subjects reporting at least one SAE.
- The number of events and the number and percentage of subjects reporting at least one AE leading to any action taken, broken down by action taken related to the product (product use interrupted, product use reduced, product use stopped, not applicable, none), treatment given (yes, no), study discontinuation, and other action taken.
- The number of events and the number and percentage of subjects reporting at least one AE related to study procedure.

An additional summary table of AEs will be also presented with a breakdown of the number of events, as well as the number and percentage of subjects reporting each AE, categorized by SOC and PT coded according to the MedDRA (version 18.0 or latest). If a subject has more than one occurrence of the same AE, the subject will be counted only once within a PT with the worst occurrence based on the presentation (*e.g.*, for presentation by severity = most severe, for presentation by relationship = most related). The number of events will be counted within each applicable category without regard to worst occurrence. For example, a subject who has the same AE three times will be counted three times in the number of events for that AE. Missing information on the intensity of AE will be counted as severe when determining the subject counts. Missing information on the relationship will be counted as related when determining the subject counts. Missing intensity and relationship will display as missing in the summary outputs when determining the number of events.

AE tables will be summarized by randomization arm and product use pattern category for the overall 12-month interval, and by randomization arm by monthly visits (Table 15.2.6.3.1). All AEs will be listed by randomization arm and product use pattern category (Listing 15.3.6.1; Tables 15.2.6.1- 15.2.6.12).

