12.6.4 Safety Analysis

All safety data collected during the study will be provided in listings by randomization arm, site, subject and product use pattern category defined over the 12-month period. Safety study periods are defined as follows:

- Screening: [Screening to V3]
- Product Trial:]V3 to V4]
- Exposure:]V4 to V16]
- Safety Follow-up: [Start to End of Safety Follow-up]

Summaries of safety parameters will be conducted on the safety population. Unless otherwise specified, summaries will be produced by randomization arm and product use pattern categories over the relevant safety exposure periods.

Adverse event data will serve as the primary assessment of safety. Other safety variables monitored in this study include: respiratory symptoms (cough assessment VAS and Likert scales); vital signs (systolic and diastolic blood pressure, pulse rate, respiratory rate); electrocardiogram (ECG) data; clinical chemistry, hematology, concomitant medications, and urine analysis safety panel; physical examination.

The number and percentage of subjects with AEs and SAEs will be tabulated by the Medical Dictionary for Regulatory Activities (MedDRA), system organ class (SOC) and preferred term (PT) for the safety population overall, and in analysis time intervals. Summaries will also be presented for AEs leading to withdrawal, AEs leading to death, AEs by relatedness to product

Confidentiality Statement

Data and information contained in this document are considered to constitute trade secrets and confidential commercial information, and the legal protections provided to such trade secrets and confidential information are hereby claimed under the provisions of applicable law. No part of this document may be publicly disclosed without the written consent of Philip Morris Products S.A.

exposure and AEs by severity. Tabulations will be performed for both the number of subjects experiencing an event and the number of events for the Safety population.

The number and percentage of subjects with clinical findings will be summarized for the safety population. Shift tables showing change from Baseline of clinical findings will be provided for: ECGs, COPD categories, and laboratory parameters (both shifts in normal ranges and toxicity grades). Descriptive statistics will be summarized by visit and change from Baseline for laboratory parameters, physical examination, ECG, respiratory symptoms, and vital signs.

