## 8 SAMPLE SIZE JUSTIFICATION

The sample size for this study was defined based on the sample size requirements of the original study, for which the sample size was calculated to ensure an overall study power of at least 90%, while maintaining at least 80% power to detect the expected effect of THS 2.2 as compared to CC for each individual endpoint of the “smokers’ health profile”, over 26 weeks of exposure. This required 475 subjects randomized per group accounting for an anticipated 75% of the THS 2.2 arm to be Mostly THS 2.2 users (i.e. report at least 70% THS 2.2 use).

Based on the assumptions that 30% of the 950 subjects will not be enrolled or will drop out from the extension study and a potential decrease from 75% to 50% of Mostly THS 2.2 users among subjects randomized to THS 2.2, the study will have at least 90% probability to determine the effect of THS 2.2 as compared to CC on FEV1 at V16 with a margin of error (95% CI) of at most  $\pm 1.5$  %pred. The anticipated SD of 6.4 %pred was estimated using the results of the “Lung Health Study” [1].

Following our current understanding of product use data in the main study, the definition of the product use categories was redefined and the underlying assumptions re-evaluated so that approximately 60% of the subjects in the THS 2.2 arm are expected to be in the THS-use category, with an anticipated 20% of subjects drop-out or reporting insufficient product use data in the two arms of the main study. Based on the 65% rate of enrollment into the extension study observed among subjects randomized in the main study, the extension study will have more than 90% probability to determine the effect of THS-use compared to CC-use on FEV1 at V16 with a margin of error (95% CI) of at most  $\pm 1.5$  %pred.

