**Table 20: Overall Product Use Pattern Categories**

1 st /2 nd 6-month Product use	THS-use	CC-use	Dual-use	ECig-use	OtherTobacco-use	Abstainer	Switcher
THS-use	THS-use	Switcher	Dual-use	Switcher	Switcher	Switcher	Switcher
CC-use	Switcher	CC-use	Switcher	Switcher	Switcher	Switcher	Switcher
Dual-use	Dual-use	Switcher	Dual-use	Switcher	Switcher	Switcher	Switcher
ECig-use	Switcher	Switcher	Switcher	ECig-use	Switcher	Switcher	Switcher
OtherTobacco-use	Switcher	Switcher	Switcher	Switcher	OtherTobacco-use	Switcher	Switcher

Abstainer	Switcher	Switcher	Switcher	Switcher	Switcher	Abstainer	Switcher
Switcher	Switcher	Switcher	Switcher	Switcher	Switcher	Switcher	Switcher

Row and columns indicates the product use categories during the first and second six months analysis periods

- For subjects who do not enroll into the extension study, or for subjects who early terminate after V10 and category is missing for the period [V10, V16[, the product use category from ]V4,V10[ will be assigned for the product use category of the 12-month randomized period.
- For analysis purposes, an over-arching category with label “Other-use” will be used to incorporate all product use categories different from THS-use, Dual-use, or CC-use. The detailed categories will be used only for the descriptive summaries of the product use over time.
- Setting to Missing the category if at least one of the categories derived for the two 6-month analysis periods is missing, apart from the subjects who early terminate after V10 and category of first 6-month period is not missing.  
For the sensitivity analysis on missing product use data (see Section 12.7.1.3.4), the category will be set to Missing only if the categories of both the two 6-month periods are set to missing, otherwise the category will be set to the non-missing category of the two 6-month periods.

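### AE percentages by 12-month product use category mix subjects followed for about 6 and about 12 months, with no adjustment for time at risk

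*SAP*

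**What the plan says.** SAP 12.7.4.2.1 sets the AE measure as "The number of events and the number and percentage of subjects reporting at least one AE", with similar lines for related, serious and severity-graded events. It then says that "AE tables will be summarized by randomization arm and product use pattern category for the overall 12-month interval". It specifies no subject-time, exposure-adjusted incidence or time to first event. Within the exposure period the only AE table split by time is Table 15.2.6.3.1, which is monthly and by randomization arm.

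SAP 10.4 defines the Safety population from all enrolled subjects with a safety value, and SAP 4.1.1 counts enrollment from V3 of the main study. SAP 12.7.4.1 covers main-study-only subjects explicitly: their safety follow-up starts "after Completion of V10 for subjects who complete the main study but do not enroll in the extension study". The exposure period is nonetheless ]V4 to V16] for everyone. The one rule that ties a denominator to the subjects at risk concerns the period after exposure: "AEs occurring during the safety follow-up will be summarized accounting for the number of subjects entered in the safety follow-up period".

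SAP 16.3.2 says that for subjects who do not enroll in the extension, the ]V4, V10[ category "will be assigned for the product use category of the 12-month randomized period". Under Table 20, THS-use in both halves is needed to stay in THS-use, and CC-use in both halves to stay in CC-use. A move between THS-use and Dual-use in either direction ends in Dual-use, and most other changes end in Switcher, which is part of Other-use.

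Protocol 12.6.4 asks for AEs to be tabulated "for the safety population overall, and in analysis time intervals".

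**The concern.** A subject seen for 12 months has about twice the opportunity to report an AE as one seen for 6. A crude percentage over a nominal 12-month interval is comparable between categories only if each has the same mix of short and long follow-up. The derivation rules work against that. A category keeps every non-enrollee it had at 6 months, because those subjects cannot change afterwards, while it loses the extension subjects who change pattern. Those lost subjects have the long follow-up. Dual-use gains some of them. Other-use gains the between-period Switchers, but it also holds subjects with missing use data, quitters and 6-month Switchers, so its average follow-up could be longer or shorter.

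The affected tables are prominent: 15.2.6.2, 15.2.6.4 and 15.2.6.6 are topline, and 15.2.6.4.1 (AEs above 5% incidence) is flagged for ClinicalTrials.gov. A reader could take a lower AE percentage in THS-use as a product effect when it reflects shorter observation, or miss a real difference masked in the same way.

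**Working it through.** The documents give no AE rate, subject-time or AE-based sample size, so there is no stated figure to reproduce. What follows is an illustration that holds the hazard identical everywhere, so that any gap is an artefact of follow-up length.

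**Inputs from the documents (SAP 8)**
- Extension entry: "Based on the 65% rate of enrollment into the extension study observed among subjects randomized in the main study". On the target of 950, that is 0.65 × 950 ≈ 618 subjects with up to 52 weeks of exposure and about 332 with at most 26.
- About 60% of the THS 2.2 arm expected in THS-use, "with an anticipated 20% of subjects drop-out or reporting insufficient product use data in the two arms of the main study".

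**Assumed inputs (not in the documents)**
- Constant AE hazard h of 3%, 6% or 10% per month in every category.
- Persistence p, the share of a category's extension entrants who keep it in the second half: 97% for CC-use, 50–75% for THS-use.
- Entry e equal in all categories: 0.65, or 0.65/0.80 = 0.8125. The second is the limiting case in which the anticipated 20% all fall outside THS-use and CC-use and none of them enters the extension.
- Dropout within each half is not modelled.

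**Formulas**
- Share of a category with 12-month follow-up: s = e·p / (1 − e + e·p)
- Mean follow-up in months: 6 + 6s
- Crude risk: s·(1 − exp(−12h)) + (1 − s)·(1 − exp(−6h))

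**THS-use against CC-use, h = 0.06** (6-month risk 0.302, 12-month risk 0.513)

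| Entry e | Category, p | s | Mean follow-up (months) | Subjects with an AE |
|---|---|---|---|---|
| 0.65 | CC-use, 0.97 | 0.6305/0.9805 = 0.643 | 9.9 | 43.8% |
| 0.65 | THS-use, 0.75 | 0.4875/0.8375 = 0.582 | 9.5 | 42.5% |
| 0.65 | THS-use, 0.50 | 0.325/0.675 = 0.481 | 8.9 | 40.4% |
| 0.8125 | CC-use, 0.97 | 0.808 | 10.8 | 47.3% |
| 0.8125 | THS-use, 0.75 | 0.765 | 10.6 | 46.4% |
| 0.8125 | THS-use, 0.50 | 0.684 | 10.1 | 44.7% |

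Over all three hazards the THS-use:CC-use ratio of percentages is 0.91–0.975 at 65% entry and 0.94–0.98 at 81%.

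**Sensitivity to entry.** Setting s equal in the two categories, with CC-use entry at 0.65, gives a break-even THS-use entry of 0.706 (p = 0.75) or 0.783 (p = 0.50). At 85% THS-use entry the ratio reverses to 1.04–1.09. With CC-use entry at 0.8125 the break-even values are 0.849 and 0.894. If entry and persistence are both equal, there is no gap.

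**THS-use against Dual-use.** Further assumptions: a share d = 15–25% of the THS 2.2 arm is in Dual-use in the first half, 90% of its entrants stay, and a fraction q = 0.5–1 of departing THS-use subjects moves to Dual-use. With a = 0.9·d·e + 0.60·e·(1 − p)·q, the Dual-use share is s = a / (a + d·(1 − e)). Mean follow-up is 10.1–11.1 months at e = 0.65 and 11.0–11.6 at e = 0.8125. The THS-use:Dual-use ratio over the whole grid is 0.82–0.97. One corner is not feasible: at 81% entry, 60% + 20% + 25% exceeds the arm. Capping d at 20% still gives 0.82–0.97.

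**What subject-time does.** Take a 6-month risk of 20%, so the 12-month risk is 1 − 0.8² = 36%. With 0%, 20%, 35% and 50% of a category seen only to V10, the crude percentage is 36.0%, 32.8%, 30.4% and 28.0%. First AEs per person-year at risk are −2·ln(0.8) = 0.446 in all four.

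**The case against.** The strongest reply has four parts.

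- **The mix can be inferred elsewhere.** Tables 15.2.1.4.1 and 15.2.1.4.1.4 give the 12-month categories for all FAS-EX subjects and for extension enrollees only, so their Ns show the extension share by category. Table 15.2.5.2 gives category counts by period in the Safety population. This stands, but those tables show only that the mix differs. They do not correct the AE percentages, and a reader of the ClinicalTrials.gov table will not have them alongside.
- **Protocol 12.6.4 may already be met.** Its sentence on time intervals does not mention product use categories, and the monthly by-arm table arguably satisfies it. This is a fair reading, so the silence of SAP Section 9 is not clear evidence of an undeclared change. The argument does not depend on it.
- **The sizes rest on chosen inputs.** That is correct. Only the 65%, 60% and 20% figures come from the documents, and at 6% per month the THS-use against CC-use gap is a few percentage points at most.
- **The safety tables are descriptive, with no formal hypotheses, and are also given by arm, where category derivation plays no part.** This limits the consequence, but the by-category versions are the ones flagged topline.

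None of these supplies a measure of time at risk in the by-category AE tables.

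**Conclusion.** The concern holds. The SAP reports crude AE percentages for a 12-month interval on denominators in which many subjects were observed for about 6 months, and its own category rules make the proportion of such subjects likely to differ between categories. That much follows from the text.

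The size and net direction do not. Under the stated assumptions the spurious THS-use:CC-use ratio runs from 0.91 to 0.98 with equal entry, and it can vanish or exceed 1 if THS-use subjects enter the extension more often. Against Dual-use it runs from 0.82 to 0.97. The figures assume a constant, common hazard and no dropout within each half. This is a reporting weakness in descriptive but prominent tables. It should be corrected, but it does not affect the primary analysis.

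**What to change.** Beside n (%), report AEs, SAEs and AEs leading to discontinuation per subject-time at risk, with mean exposure time, by arm and by product use category. State the convention: time to first event when counting subjects, total time at risk when counting events.

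As an alternative or an addition, split the by-category AE tables into ]V4, V10] and ]V10, V16], with the subjects entering each period as the denominator. This also provides time intervals by category and does not rely on a constant hazard. The SAP should then say which category applies in the first half. Section 10.4 implies the 12-month category, which classifies early AEs partly by later product use, and a footnote should say so.

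Apply the same to the by-category SAE and discontinuation tables when their threshold of 10 events is reached.

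The cost is one or two extra columns, or a period split, in tables already planned, using dates already collected. Subject-time removes only the follow-up-length component. The categories remain post-randomization and self-selected, so the rates are still descriptive.

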#### 3.1 Revision History

Version	Date of Revision	Revision
2.0	08-Dec-2017	
 
○ Updated Table 3 and footnotes to clarify covariates used
 
○ Updated Sections 9, 12.7.1, 12.7.2, and 12.7.3 to indicate that results from inferential analyses will be presented at Months 3 and 6 also
 
○ Updated Section 9 to indicate that p-values will not be calculated in the analysis of need to cough
 
○ Updated Section 10.2 to clarify that analyses will be conducted using time-varying product use categories
 
○ Clarified in Section 10.4 that safety analyses will be performed on 12-month product use categories
 
○ Updated Section 11.1 to clarify how major PDs are handled
 
○ Added text to Section 12.1.4 to clarify handling of parameters with values below LLOQ in the denominator of the ratio
 
○ Clarified in Section 12.3 that analyses will be presented for 6-month and/or 12-month product use pattern categories
 
○ Clarified in Section 12.7.1.2 that the evaluated
 

Version	Date of Revision	Revision

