**Table 1: Actual Product Use General Pattern Categories**

Category Label	General Description
THS-use	
 
• ≥ 1 THSts or CC and
 
• ≥ 70% THSts use over the entire analysis period and
 
• ≥ 70% THSts use on ≥ 50% of the days in the analysis period
 

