**Table 1: Actual Product Use General Pattern Categories**

Category Label	General Description
Dual-use	
 
• <math>\geq 1</math> THSts or CC and
 
• <math>1\% \leq</math> THSts <math>< 70\%</math> over the entire analysis period or
 
• THS-use and CC-use don't apply due to <math>< 50\%</math> of the days
 

CC-use	
 
• <math>\geq 1</math> THSts or CC and
 
• <math>< 1\%</math> THSts over entire analysis period and
 
• <math>< 1\%</math> THSts on <math>\geq 50\%</math> of the days in analysis period
 

Other-use	General category encompassing subjects with missing product use, or subjects using e-cigarettes or other tobacco products, subjects who quit, or subjects who switched across different use patterns between consecutive analysis periods.

Details of the product use categories are reported in Appendix 16.3 "Data Handling and Derivation of Product Use Pattern Categories". THSts = THS Tobacco Stick; THS=Tobacco Heating System; CC= Conventional Cigarette.

Full details of the product use categories derivation are reported in Appendix 16.3 "Data Handling and Derivation of Product Use Pattern Categories".

General product use categories will be used for both safety summaries and non-safety analysis. More granular product exposure categories will be used for the detailed description of the product use patterns observed in the study.

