### 10.4 Safety Population

The Safety population consists of all the subjects enrolled with signed ICF who have at least one valid value for a safety assessment. This analysis set excludes all subjects enrolled in sites terminated due to findings of non-compliance with GCP and/or with the protocol. In general, the exposure assignment for the Safety population will be by randomization arm and according to the product use pattern categories (J[V4, V16]) as defined in Section 4.1.2 “Definition of Product Use Pattern Categories”.

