Table 15.2.4.8.3	Analysis of Additional Cardiovascular Disease Markers – FAS-AR			
Table 15.2.4.9.1	Summary of Cough Assessment Over Study – FAS-EX			
Table 15.2.4.9.2	Summary of Cough Assessment Over Study – PP Population			
Table 15.2.4.10	Analysis of Proportion of Subjects Reporting Need to Cough Over Study – FAS-EX			
Table 15.2.4.11.1	Descriptive Statistics of MCEQ Subscales – FAS-EX			
Table 15.2.4.11.2	Descriptive Statistics of MCEQ Subscales – PP Population			

Table No.	Title	Topline (Y/N)	Safety (Y/N)	Clinical Trial.gov (Y/N)
Table 15.2.4.12.1	Analysis of MCEQ Subscales – FAS-EX			
Table 15.2.4.12.2	Analysis of MCEQ Subscales – PP Population			
Table 15.2.4.13.1	Descriptive Statistics of FTND Results – FAS-EX			
Table 15.2.4.13.2	Descriptive Statistics of FTND Results – PP Population			
Table 15.2.4.14.1	Descriptive Statistics of Intent to Use THS 2.2 Questionnaire – FAS-EX			
Table 15.2.4.14.2	Descriptive Statistics of Intention to Use THS 2.2 Questionnaire – PP Population			
Table 15.2.4.15	Descriptive Statistics of Distribution of Dual Use over Randomized Exposure Period – FAS-EX			
Table 15.2.4.16	Analysis of Final Propensity Model – FAS-AR			
Table 15.2.4.17	Analysis of Exposure-Response Relationship of Dual Use – FAS-AR			
Table 15.2.5.1	Summary of Product Use Pattern – FAS-EX	Y		

Table No.	Title	Topline (Y/N)	Safety (Y/N)	Clinical Trial.gov (Y/N)
Table 15.2.5.1.1	Summary of Product Use Pattern by Sex - FAS-EX			
Table 15.2.5.1.2	Summary of Product Use Pattern by Consumption Level - FAS-EX			
Table 15.2.5.2	Summary of Product Use Pattern - Safety Population			
Table 15.2.5.3	Summary of Product Use Pattern - FAS-AR	Y		
Table 15.2.5.4	Summary of Detailed Product Use Pattern - FAS-EX			
Table 15.2.6.1	Summary of Adverse Events – Safety Population		Y	
Table 15.2.6.2	Summary of Adverse Events by Product Use Pattern Category – Safety Population	Y	Y	
Table 15.2.6.3	Summary of Adverse Events by System Organ Class and Preferred Term – Safety Population		Y	
Table 15.2.6.3.1	Summary of Monthly Adverse Events by System Organ Class and Preferred Term – Safety Population		Y	
Table 15.2.6.4	Summary of Adverse Events by Product Use Pattern Category, System Organ Class and Preferred Term – Safety Population	Y	Y	

Table No.	Title	Topline (Y/N)	Safety (Y/N)	Clinical Trial.gov (Y/N)

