Table 15.2.6.4.1	Summary of Frequent Adverse Events (Incidence >5%) by System Organ Class and Preferred Term and Product Use Category– Safety Population		Y	Y
Table 15.2.6.5	Summary of Adverse Events by System Organ Class, Preferred Term and Relationship to Study Product Exposure and Expectedness – Safety Population		Y	
Table 15.2.6.6	Summary of Adverse Events by Product Use Pattern Category, System Organ Class, Preferred Term and Relationship to Study Product Exposure and Expectedness – Safety Population	Y	Y	
Table 15.2.6.7	Summary of Adverse Events Leading to Study Product Discontinuation, Interruption, or Reduction by System Organ Class and Preferred Term – Safety Population		Y	
Table 15.2.6.8	Summary of Adverse Events Leading to Study Product Discontinuation, Interruption, or Reduction by Product Use Pattern Category, System Organ Class, and Preferred Term – Safety Population		Y	
Table 15.2.6.9	Summary of Adverse Events Related to Study Procedure by System Organ Class and Preferred Term – Safety Population		Y	

Table No.	Title	Topline (Y/N)	Safety (Y/N)	Clinical Trial.gov (Y/N)
Table 15.2.6.10	Summary of Adverse Events Related to Study Procedure by Product Use Pattern Category, System Organ Class and Preferred Term – Safety Population		Y	
Table 15.2.6.11	Summary of Adverse Events by System Organ Class, Preferred Term and Severity – Safety Population		Y	
Table 15.2.6.12	Summary of Adverse Events by Product Use Pattern Category, System Organ Class, Preferred Term and Severity – Safety Population		Y	
Table 15.2.6.13	Summary of Serious Adverse Events by System Organ Class and Preferred Term – Safety Population		Y	
Table 15.2.6.14	Summary of Serious Adverse Events by Product Use Pattern Category, System Organ Class and Preferred Term – Safety Population		Y	
Table 15.2.6.15	Summary of Adverse Events Leading to Study Discontinuation by System Organ Class and Preferred Term – Safety Population		Y	
Table 15.2.6.16	Summary of Adverse Events Leading to Study Discontinuation by Product Use Pattern Category, System Organ Class and Preferred Term – Safety Population		Y	

Table No.	Title	Topline (Y/N)	Safety (Y/N)	Clinical Trial.gov (Y/N)
Table 15.2.6.17	Summary of THS 2.2 Device Events – Safety Population		Y	
Table 15.2.6.18	Summary of Clinical Chemistry Parameters – Safety Population		Y	

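### The AE tables marked for topline and ClinicalTrials.gov are all by a product-use category that an AE can change, so their THS-use column can under-represent subjects who did not tolerate THS 2.2

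*SAP*

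**What the plan says.** SAP 10.4 says that "the exposure assignment for the Safety population will be by randomization arm and according to the product use pattern categories", with the category taken over ]V4, V16[. The revision history confirms this as a deliberate choice: "Clarified in Section 10.4 that safety analyses will be performed on 12-month product use categories". SAP 12.7.4.2.1 applies it to adverse events: "AE tables will be summarized by randomization arm and product use pattern category for the overall 12-month interval". Monthly AEs are by arm only.

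THS-use requires, among other conditions, "≥ 70% THSts use over the entire analysis period". Other-use takes in, among others, "subjects who quit, or subjects who switched across different use patterns between consecutive analysis periods", and also subjects with missing product use. SAP 16.3.2 weights later diary days more heavily. Its Table 20 turns THS-use followed by CC-use into Switcher, which is analysed as Other-use, and THS-use followed by Dual-use into Dual-use.

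SAP 16.3.2 also carries categories forward. A subject who terminates after V7 keeps the ]V4, V7] category, and one who terminates after V10 keeps the last category available. A subject who does not enrol in the extension keeps the ]V4, V10[ category.

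In SAP 16.4 the AE tables flagged for topline are 15.2.6.2 ("Summary of Adverse Events by Product Use Pattern Category"), 15.2.6.4 and 15.2.6.6. The only AE table flagged for ClinicalTrials.gov is 15.2.6.4.1 ("Summary of Frequent Adverse Events (Incidence >5%) by System Organ Class and Preferred Term and Product Use Category"). All four are by category. Their by-arm counterparts 15.2.6.1, 15.2.6.3 and 15.2.6.5 carry the safety-reporting flag only, and no by-arm version of 15.2.6.4.1 is listed.

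**The concern.** The column in which an AE is counted depends on what the subject used after the AE. If an event leads a THS user to stop or cut down, that behaviour can move the subject, and the event, out of THS-use. The column then describes mainly people who kept using THS 2.2, while objective 10 asks for the safety profile associated with the product. Unequal follow-up is a separate matter: this would happen with complete 12-month follow-up.

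Appendix 16.2 justifies analysis by actual use on the ground that tobacco use is driven by factors other than perceived product effects, and its argument is about the smokers' health profile endpoints. Symptomatic AEs are effects that a subject notices and may act on, so that reasoning does not carry over to safety. The SAP also moved FAS-EX to 6-month categories for Months 1–6 (sections 9 and 10.2) but kept the 12-month category for safety. For a subject in the extension, an AE in Month 2 is therefore classified partly by product use in Month 11.

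**Working it through.** **Inputs.** Nominal visit days come from SAP Table 17: V4 = 1, V7 = 92, V10 = 183, V13 = 274, V16 = 365. The weights, the 70%, 1% and 50% rules, the missing-data rule and carry-forward come from SAP 16.3.1–16.3.2, and the combination of half-years from Table 20. Assumptions: 20 THS sticks a day and no cigarettes before the stop, then a complete change on one day. Stop days 5 to 364 were each classified (360 possible days).

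**Early stop, change to cigarettes, stays in study.** The first quarter is days 2–92: 91 days, weights 1 to 91, sum 91 × 92 / 2 = 4186. With k days on THS the weighted THS share is [k(k+1)/2] / 4186.
- k = 8 (stop on day 10): 36 / 4186 = 0.86%, below 1%, so CC-use.
- k = 9 (stop on day 11): 45 / 4186 = 1.07%, so Dual-use in that quarter. It is followed by CC-use, which gives Switcher.

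**Late stop, same route.** In the second half-year, days 183–274 have weight 1 (92 days) and days 275–364 have weights 1 to 90 (sum 4095), total 4187. With k THS days after V13 the THS share is [92 + k(k+1)/2] / 4187.
- k = 74: 2867 / 4187 = 68.5%, so Dual-use.
- k = 75 (stop on day 350): 2942 / 4187 = 70.3%, so THS-use.

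Only stops on days 350–364, 15 days, leave this subject in THS-use.

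**All stop days, three routes.**

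| After the stop | THS-use | Dual-use | Other-use | CC-use |
|---|---|---|---|---|
| Smokes cigarettes, stays | 15 (4%) | 66 | 273 | 6 |
| Quits all tobacco, stays | 27 (7.5%) | 43 | 290 | 0 |
| Terminates the study | 273 (76%) | 0 | 87 | 0 |

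Other-use in the second row is 273 Switcher plus 17 Abstainer. In the third row it is the 87 stop days before V7, where the category is Missing; every stop from V7 on stays in THS-use. These are shares of possible stop days, not of subjects.

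**Size.** Let r be the proportion of the THS arm that stops for an AE. The documents give no value, so r = 5% is an assumption, with range 2–10% and stops spread evenly over the days examined.
- All terminate: r × 87/360 = 1.2 points of the arm (0.5 to 2.4).
- All switch to cigarettes and stay: r × 345/360 = 4.8 points (1.9 to 9.6).

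Of 475 randomised, 5% is about 24 subjects, of whom about 6 and 23 respectively would leave the column.

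**Which route applies.** Protocol 6.2.2 sends a subject whose study product is discontinued to early termination procedures. Protocol 5.2 says that use of another tobacco or nicotine product does not lead to discontinuation, 6.2 leaves subjects free to stop their product at any time, and 6.2.1 keeps quitters in the study. SAP 12.7.4.2.1 lists product use stopped, interrupted or reduced separately from study discontinuation, so it expects both. The texts do not settle which route an AE-driven stopper follows.

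**The case against.** The best defence is that nothing is missing. The main AE tables come in pairs, by arm and by category (15.2.6.1/.2 through 15.2.6.11/.12). SAEs and AEs leading to discontinuation are by arm by default, and by category only with at least 10 events (SAP 12.7.4.2.2–12.7.4.2.3). Topline is an early extract for sponsor management (13.3), the registry tables are only candidates for publication (13.5), and the final analyses include every listed table (13.4). All of this stands. It limits the point to what the headline outputs show.

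The second defence is Protocol 6.2.2 with carry-forward: on that route most stop days remain in THS-use. This also stands, and it rules out several stronger inferences a reader might draw:
- That every AE-driven stopper leaves THS-use. Those who terminate from V7 on do not, nor do those who stop in the last two to four weeks and stay.
- That 4.8 points applies to all AE-driven stoppers. It is only the switch-and-stay route.
- That the THS-use column of Table 15.2.6.8 ("Summary of Adverse Events Leading to Study Product Discontinuation, Interruption, or Reduction by Product Use Pattern Category") is nearly empty by construction. Terminators after V7 remain in it, and an interruption or reduction need not change the category.
- That the category is a 12-month one for everyone. About 35% of randomised subjects (65% enrolled in the extension, SAP 8) carry a 6-month category.
- That THS events are commonly counted as cigarette events. CC-use arises for 6 of 360 stop days, and relatedness to THS 2.2 and to CC is reported separately.

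Subjects who leave the column also leave its denominator, so the points above are not a bias in any reported AE percentage. CC-arm subjects who quit or change product after an AE leave CC-use too, so the direction of a THS-use versus CC-use comparison is not established. The table shells are a separate document, and category columns split by arm would lessen the problem.

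**Conclusion.** The concern holds in a limited form. The safety category is post-randomisation and can be altered by the AE it is used to describe, and no by-arm AE table is flagged for topline or the registry. The headline THS-use column can therefore under-represent subjects who did not tolerate THS 2.2.

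The mechanism follows from the SAP's own rules. The size does not: it depends on an unknown rate of AE-driven stopping, on its timing, and on whether such subjects stay. Even timing is itself an assumption. If stops cluster before V7, the loss on the termination route approaches the full stopping rate, because every such stop becomes Missing. The effect on reported AE percentages cannot be derived from the documents. The point merits a change mainly because the randomised comparison is already being produced and only needs to be placed where it will be read.

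**What to change.** In SAP 16.4, flag by-arm Tables 15.2.6.1, 15.2.6.3 and 15.2.6.5 for topline, and add a by-arm version of 15.2.6.4.1 flagged for ClinicalTrials.gov. Keep the by-category tables alongside them, with a footnote that the category includes product use after AE onset.

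Optionally, add a supportive version of Table 15.2.6.8 that attributes each AE leading to product stop, interruption or reduction to the category in use up to onset, built from the per-day categories in SAP Table 19. Its denominator must be defined, since one subject can then appear in several columns, and so must the handling of partial AE dates, which SAP 12.1.4 does not impute.

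Reconcile Protocol 6.2.2 with Protocol 5.2, 6.2 and 6.2.1 on whether a subject who stops the product stays in the study, and state in the SAP how each case is categorised.

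The cost is changed flags, one or two extra tables, and a THS AE profile that may look less favourable. No new data are needed.
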